8.3.4. Subgroup Analysis in Subjects with Comorbid Asthma

Statistical analyses will be carried out for subjects who have comorbid asthma.

8.3.4.1. Asthma Subjects: NPS

The primary endpoint analysis of NPS will be repeated among subjects with comorbid asthma.

As was done for the primary endpoint, summary statistics will be provided for the subgroup of subjects with comorbid asthma, for baseline, each time of measurement, and for changes from baseline.

For subjects with comorbid asthma only, statistical analysis of NPS will employ an MMRM where the change from baseline in NPS at Weeks 4, 8, 12 and 16 values are modeled using the baseline (Day 1) value as a covariate; treatment (3 levels), time (Weeks 4, 8, 12 and 16), and treatment by time interaction as fixed effect factors; and subject (the repeated measures) as random effect in the model.

8.3.4.2. Asthma Subjects: SNOT-22

The primary endpoint analysis of SNOT-22 will be repeated among subjects with comorbid asthma. The same summary statistics and analyses described in 8.3.4.1 for NPS will be repeated for SNOT-22.

8.3.5. Change in the Percentage of Volumetric Maxillary Sinus Occupied by Disease (VMSOD)

At clinic visits on Day 1 and Week 16/EOT, computed tomography (CT) scans are used to calculate the volume of the air (mL), the volume of the mucosa (mL), the % occupied by disease, and the thickness of the lateral wall. Central reading before Day 1 (Visit 2) will be used for comparison with the EOT reading. The sites will remove subject-identifying information from the imaging data header prior to sending the imaging data to the central reader.

The percentage occupied by disease will be analyzed. Baseline is defined as the percentage of VMSODs on Day 1. The Week 16/EOT value is the % of VMSOD at the Week 16/EOT assessment. For each subject, the difference in the % VMSOD between the Week 16/EOT and baseline values will be calculated (EOT value minus baseline value) as a measure for the percent change in opacification.

Summary statistics for % of VMSOD for baseline value, Week 16/EOT value, and the change from baseline (Week 16/EOT minus baseline) will include n, mean, standard deviation, median, minimum, and maximum. For each treatment arm, a Wilcoxon signed ranks test will be used to assess whether the change from baseline is statistically significant.

Statistical analysis of the change in % VMSOD from baseline at Week 16/EOT will be performed using ANCOVA with baseline % VMSOD as a continuous covariate, and treatment (3 levels) as a factor. Gender (M/F) may be considered for inclusion in the model. If preliminary analysis shows the gender-by-treatment interaction term to be not significant at alpha=0.05, the gender-by-treatment term will be dropped out of the model. The final model may include main effect for gender if this is deemed important to adjust for.

Least squares adjusted means from the final ANCOVA model will be used to perform pairwise comparisons of each etokimab dosing regimen with the Placebo group. An estimate of treatment difference and accompanying 95% confidence intervals will be produced from the model.

Each (two-sided) comparison of an etokimab dose group with the Placebo group with respect to % VMSOD will use the 5% level of significance. It is expected that treatment with etokimab will lead to lower % VMSOD values at week 16/EOT than observed at baseline. A statistically significantly higher adjusted mean score for an etokimab group compared to the Placebo group will be regarded as evidence of efficacy for etokimab compared to Placebo.

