8.1.8 QUALITY OF LIFE ASSESSMENTS

8.1.8.1 SHORT FORM 36 HEALTH SURVEY (SF-36)

The SF-36 is a generic questionnaire measuring general health status (QoL) in the last 4 weeks before completing the questionnaire. The SF-36 is a 36-item questionnaire that measures 8 multi-item dimensions of health: physical functioning (10 items) social functioning (2 items) role limitations due to physical problems (4 items), role limitations due to emotional problems (3 items), mental health (5 items), energy/vitality (4 items), pain (2 items), and general health perception (5 items).

For each dimension, item scores are coded, summed, and transformed on to a scale from 0 (worst possible health state measured by the questionnaire) to 100 (best possible health state). Two standardized summary scores can also be calculated from the SF-36; the physical component summary and the mental health component summary. The time for completion is 5 to 10 minutes.

The SF-36 will be completed as indicated in the SoA (see Section 1.3) and is located on the clinical tablet.

A sample SF-36 is provided in Appendix F.

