APPENDIX F: SAMPLE SHORT FORM 36 HEALTH SURVEY (SF-36)

Your Health and Well-Being

This survey asks for your views about your health. This information will help keep track of how you feel and how well you are able to do your usual activities. Thank you for completing this survey!

For each of the following questions, please mark an \boxtimes in the one box that best describes your answer.

1. In general, would you say your health is:

2. Compared to one year ago, how would you rate your health in general now?

Much better now than one year ago	Somewhat better now than one year ago	About the same as one year ago	Somewhat worse now than one year ago	Much worse now than one year ago
_	\blacksquare	lacksquare	lacktriangle	V

SF-36v2TM Health Survey © 1996, 2000 by QualityMetric Incorporated and Medical Outcomes Trust. All Rights Reserved. SF-36® is a registered trademark of Medical Outcomes Trust. (SF-36v2 Standard, US Version 2.0)

3. The following questions are about activities you might do during a typical day. Does your health now limit you in these activities? If so, how much?

	Yes, limited a lot	Yes, limited a little	No, not limited at all	
	lacktriangle	lacktriangle	lacktriangle	•
 Vigorous activities, suc heavy objects, participa sports 	ting in strenuou	IS		
Moderate activities, such pushing a vacuum clear playing golf	er, bowling, or			
. Lifting or carrying groce	nies			
d Climbing several flights	of stairs			
« Climbing one flight of st	airs			
Bending, kneeling, or sto	oping			
« Walking more than a mi	le			
h Walking several hundred	l yards			
Walking one hundred ya	r ds			
Bathing or dressing your	self			П

SF-36v2™ Health Survey © 1996, 2000 by QualityMetric Incorporated and Medical Outcomes Trust. All Rights Reserved. SF-36® is a registered trademark of Medical Outcomes Trust. (SF-36v2 Standard, US Version 2.0)

4. During the past 4 weeks, how much of the time have you had any of the following problems with your work or other regular daily activities as a result of your physical health?

[figure not shown]
			Some of the time		None of the tim
Cut down on the amount of time you spent on work or other activities		🗀 2	🗀	🗀 4.	
Accomplished less than you would like		🔲 2		🗆4	
Were limited in the kind of work or other activities		2	🔲 1	🗀 4	
Had difficulty performing the work or other		🗀 2	🗀 3	🗀 4	[]

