*UPSIT only. Lund-MacKay score is not assessed at Week 8.

**UPSIT and Lund-MacKay scores do allow gaps between analysis visits.

Table 2f: Visit Windows for Assigning PW Visits to an Analysis Visit for EQ-VAS, Nocturnal Awakenings, and NPIF

Study Period	Visit	Target Day*	Window for Reassignment to Scheduled Visit
Baseline	Baseline	1	≤ 1
Treatment Period	Week 1	5	2-7
	Week 2	11	8-14
	Week 3	18	15-21
	Week 4	25	22-28
		•••	
	Week 16/EOT	102	99-105
Safety Follow-up Period	Week 20	130	127-133
	Week 24/EOS/ETV**	158	155-161

*Except for Week 1, Target Day for the rest weekly analysis visits is the mid-week day.

**The last observation in the time window will be used. [This is an exception from the rule regarding closest to target.]

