8.3. Exploratory Efficacy Endpoints

8.3.1. Patient Reported Quality of Life Scales

8.3.1.1. Medical Outcomes Study 36-item Short Form (SF-36)

The SF-36 is a generic health survey with 36 items (Ware et al. (1992); Hays et al. (1993)) that measure functional health and well-being from the subject's perspective and will be assessed during clinic visits on Day 1 and Weeks 4, 8, 12, 16 and 24. The 36 questions are grouped into 11 sections of questions in the questionnaire. Some of the sections consist of multiple questions. The 36-item patient-reported questionnaire covers eight health domains: physical functioning (10 items), bodily pain (2 items), role limitations due to physical health problems (4 items), role limitations due to personal or emotional problems (4 items), emotional well-being (5 items), social functioning (2 items), energy/fatigue (4 items), and general health perceptions (5 items).

To specify scoring formulas, the 11 sections of the SF-36 are denoted by Q1 to Q11 according to the order in the questionnaire and the individual items in each question are denoted by their alphabetic order. These may be restated into items 1 to 36 (Please refer to Appendix 19.1).

Scores for each domain range from 0 to 100, with a higher score defining a more favorable health state. The 8 scaled scores are weighted sums of the questions in each section. Scores range from 0 - 100, with lower scores indicating more disability and higher scores indicating less disability. The 8 dimensions/scales are: Physical functioning (PF), Role limitations due to physical health (RP), Role limitations due to emotional problems (RE), Energy/Fatigue (or, Vitality) (VT), Emotional Well-being (or, Mental Health) (MH), Social functioning (SF), Pain (BP), and General Health (GH).

From the eight health dimensions, a physical component summary (PCS), which is the aggregate score of the PF; RP; BP and GH scales, and mental component summary (MCS) which is the aggregate score of the VT; SF; RE and MH scales, measures may be derived. No total score will be derived. (Lins L. et al. (2016)).

Summary statistics for each of the 8 domains and for the PCS and MCS for Day 1, and Weeks 4, 8, 12, 16, and 24 will include n, mean, standard deviation, median, minimum and maximum for baseline, the time of measurement, and the change from baseline.

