The etokimab dose groups will be compared to the Placebo group during the treatment period (up to Week 16) only. The values obtained between Week 17 and Week 24will not be included in the efficacy analysis, as follow-up is intended for safety only.

Statistical analysis of morning/evening NPIF during the treatment period will employ an MMRM, where the change from baseline in Weeks 4, 8, 12 and 16 AM (PM) NPIF values are modeled using the baseline value as a covariate; treatment (3 levels), stratification factor, treatment by stratification factor, categorical time (Weeks 4, 8, 12 and 16), and treatment by time interaction as fixed effect factors; and subject (the repeated measures) as random effect. The analysis is similar to that performed for the NPS and SNOT-22 scores.

The primary time point for the analysis of morning/evening NPIF is Week 16. The Week 16 least squares adjusted means from the MMRM will be used to perform pairwise comparisons of each etokimab dosing regimen with the Placebo group. An estimate of treatment difference and accompanying 95% confidence intervals will be produced from the model. It is expected that treatment with etokimab will lead to higher AM/PM NPIF values at Week 16 than obtained at baseline. A statistically significant difference (P<0.05) where the least squares means for the etokimab group is higher than for the Placebo group will be regarded as evidence of efficacy for etokimab compared to Placebo.

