19. APPENDICES

19.1. Scoring the SF-36

Item (Question) Number	Number of	Cumulative Question
	Questions	Number or Range
1	1	1
2	1	2
3	10 (a-j)	3-12
4	4 (a-d)	13-16
5	3 (a-c)	17-19
6	1	20
7	1	21
8	1	22
9	9 (a-i)	23-31
10	1	32
11	a-d	33-36

Scoring the SF-36: Step 1 - Recoding Items

Item numbers	Change Original	To recoded value of:
	Response	
	Category*	
1, 2, 20, 22, 34, 36	1→	100
	2→	75
	3→	50
	$4 \rightarrow$	25
	5→	0
3, 4, 5, 6, 7, 8, 9, 10, 11, 12	1>	0
	2→	50
	3→	100
13, 14, 15, 16, 17, 18, 19	1→	0
	2→	100
21, 23, 26, 27, 30	1>	100
	2→	80
	3→	60
	4→	40
	5→	20
	6 →	0
24, 25, 28, 29, 31	1>	0
	2→	20
	3→	40
	4→	60
	5→	80
	6 →	100
32, 33, 35	1>	0

Statistical Analysis Plan for Interventional Studies Sponsor: Anaptys Bio Inc.; Protocol No.: ANB020-006

2→	25
3→	50
$4 \rightarrow$	75
5→	100

*Precoded response choices as printed in the questionnaire

Scoring the SF-36: Step 2 – Averaging Items to Form Scales

Scale	Number of	After recoding average the	Item numbers on
	Items	following items	original questionnaire
Physical functioning	10	3, 4, 5, 6, 7,8, 9, 10, 11, 12	Qu. 3 a-j
Role limitations due to	4	13, 14, 15, 16	Qu. 4 a-d
physical health			
Role limitations due to	3	17, 18, 19	Qu. 5 a-c
emotional health			
Energy/fatigue	4	23, 27, 29, 31	Qu. 9 a, e, g, i
Emotional well-being	5	24, 25, 26, 28, 30	Qu. 9 b, c, d, f, h
Social functioning	2	20, 32	Qu. 6; Qu. 10
Pain	2	21, 22	Qu. 7; Qu.8
General health	5	1, 33, 34, 35, 36	Qu. 1; Qu. 11 a-d

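### Three SAP rules for exploratory endpoints are wrong or in conflict as written: the %VMSOD efficacy direction, the SF-36 scoring key, and the Week 16 diary window

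*SAP*

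**What the plan says.** **%VMSOD (SAP 8.3.5).** Change is the Week 16/EOT value minus baseline, analysed by ANCOVA with two-sided 5% comparisons. The expected direction is "It is expected that treatment with etokimab will lead to lower % VMSOD values at week 16/EOT than observed at baseline". The next sentence gives the rule: "A statistically significantly higher adjusted mean score for an etokimab group compared to the Placebo group will be regarded as evidence of efficacy". SAP 8.3.3 has a closely similar rule for nasal peak inspiratory flow (NPIF), a measure on which higher is better: a significant difference "where the least squares means for the etokimab group is higher than for the Placebo group will be regarded as evidence of efficacy".

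**SF-36 (SAP 8.3.1.1 and 19.1; Protocol 8.1.8.1 and Appendix F).** SAP 8.3.1.1 says "Scores for each domain range from 0 to 100, with a higher score defining a more favorable health state". The key in 19.1 recodes the role items ("13, 14, 15, 16, 17, 18, 19") as 1→0 and 2→100, and the Q9 items (23-31) on six levels. The sample form in Appendix F is marked "SF-36v2 Standard, US Version 2.0" and prints five responses for Q9. Protocol 8.1.8.1 says only: "The SF-36 will be completed as indicated in the SoA (see Section 1.3) and is located on the clinical tablet". It does not name the version.

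**Diary windows (SAP 6.4, Table 2f).** The text maps weekly and daily data to consecutive analysis weeks from Day 1 through Week 24. The footnote adds: "Except for Week 1, Target Day for the rest weekly analysis visits is the mid-week day". Weeks 1-4 are printed as Days 2-7, 8-14, 15-21 and 22-28. After an ellipsis come Week 16/EOT as Days 99-105 (target 102), Week 20 as 127-133 (130) and Week 24 as 155-161 (158). Both the text and the table title list EQ-VAS among these data. Table 2a covers the QoL instruments, with Week 16 as Days 99-126.

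SAP Section 12 lists one departure from the protocol, on nocturnal awakenings. It explains none of these points.

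**The concern.** A programmer or report writer following the text literally would go wrong in three places.

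- **%VMSOD:** the pre-specified conclusion has the opposite sign to the stated expectation. The wording was probably carried over from NPIF.
- **SF-36:** if the tablet holds version 2, some role responses have no score and others are scored the wrong way. The error passes into the physical and mental component summaries (PCS and MCS), which are modelled by MMRM.
- **Table 2f:** NPIF is assigned to weeks by date and its primary time point is Week 16, so the table decides which seven days are analysed. The rhinosinusitis VAS, which is the scale collected weekly (SAP 8.3.1.3), appears in no window table. EQ-VAS, collected at clinic visits, appears under two.

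All of these endpoints are exploratory. At stake is whether the exploratory results mean what their labels say, and whether any correction is made before unblinding.

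**Working it through.** **1. %VMSOD direction.** Write d = (etokimab change) − (placebo change), with change = EOT − baseline. Less disease is better, so benefit means d < 0. The SAP rule requires d > 0. With made-up values:

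- Changes of −20 (etokimab) and −5 (placebo): d = −15. This is a benefit, and it fails the rule.
- Changes of +5 and −5: d = +10. This is a worsening, and it meets the rule.

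Reading the adjusted mean as a size of reduction does not rescue the rule, because the section fixes the sign convention. The comparison is two-sided, so the estimate, CI and p-value do not depend on the sentence.

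**2. SF-36 key applied to responses coded 1-5.** Positively worded Q9 items score 100, 80, 60, 40, 20; negatively worded items score 0, 20, 40, 60, 80.

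- Energy (23, 27 positive; 29, 31 negative): minimum (2×20 + 2×0)/4 = 10; maximum (2×100 + 2×80)/4 = 90.
- Emotional well-being (26, 30 positive; 24, 25, 28 negative): minimum (2×20 + 3×0)/5 = 8; maximum (2×100 + 3×80)/5 = 88.
- Role items: responses 3, 4 and 5 have no score. Response 2 (limited most of the time) scores 100, the best value.

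The SAP states a range of 0-100 for every scale. Scale items total 10+4+3+4+5+2+2+5 = 35. Affected items are 7 role items plus 9 Q9 items = 16, and 16/35 = 46%. Four of eight scales are touched: one of the four behind PCS (role-physical) and three of the four behind MCS (vitality, role-emotional, mental health).

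**3. Table 2f.** The first rows follow Week k = Days 7(k−1)+1 to 7k, with mid-week day 7(k−1)+4. (Week 1 starts on Day 2 because Day 1 is baseline.) This reproduces the windows for Weeks 1-4 and the targets 11, 18 and 25 for Weeks 2-4. It does not reproduce the later rows:

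| Label | Printed days (target) | Days by the rule (target) | Printed days are |
|---|---|---|---|
| Week 4 | 22-28 (25) | 22-28 (25) | Week 4 |
| Week 16 | 99-105 (102) | 106-112 (109) | Week 15 (105/7) |
| Week 20 | 127-133 (130) | 134-140 (137) | Week 19 (133/7) |
| Week 24 | 155-161 (158) | 162-168 (165) | Week 23 (161/7) |

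Weekly rows hidden by the ellipsis cannot close the gap. Days 29-98 are 70 days, or 70/7 = 10 windows, while Weeks 5-15 need 11. Where the shift begins is not visible. From Week 16 onward it is constant: Days 106-126 are 21 days, three windows for Weeks 17-19. Days 106-112 would therefore be labelled Week 17, and SAP 8.3.3 leaves Weeks 17-24 out of the efficacy analysis. By SAP 6.2.3 the treatment period ends the day before Visit 7. At the Day 113 target that is Day 112, so the omitted week is the last week of treatment. Days 162-168 have no window at all.

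**4. EQ-VAS.** The Week 16 visit falls on Day 113±5, that is Days 108-118. None of these days lies in Table 2f's 99-105; all lie in Table 2a's 99-126.

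**The case against.** The strongest case is one of weight: these are separate drafting slips on exploratory endpoints, and the arithmetic is not in dispute.

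- **%VMSOD.** The sentence before the rule states the expected direction and the results are two-sided, so a careful reader would probably notice. That stands as to practical risk. The written rule is still wrong.
- **SF-36.** Appendix F is only a sample. The SAP cites the RAND 36-item survey 1.0 and the 1992 paper introducing the instrument, which points to an earlier form that the key may fit. This bears on the conflict, but a citation does not show what was loaded on the tablet. The Q4 and Q5 grids are also damaged in the text copy, and the label for response 2 is read across from Q9. The Q4 remnant still shows five columns, with the middle option third and the none option fifth. The point is therefore rightly conditional on version 2.
- **Table 2f.** The text of 6.4, followed alone, gives the right weeks, so the harm arises only if the table prevails. The ten-for-eleven count assumes that the unseen rows are seven days wide. Both are fair qualifications, but table and text then contradict each other and nothing says which governs. The Week 20 and 24 rows do not affect NPIF efficacy. The shift applies to all arms, so no bias in the treatment contrast can be claimed.
- **EQ-VAS.** This is probably a single naming slip, and scheduled visits may be analysed under their eCRF label. The rhinosinusitis VAS is covered in substance by the weekly rule, though it is not named.
- **Early attenders.** Visit 7 may fall on Day 108, and follow-up starts on that date, so a corrected window of Days 106-112 can overlap follow-up. This is a real gap and the fix should address it.

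**Conclusion.** The concern holds: the rules are wrong or in conflict as written. The co-primary and hierarchical secondary tests are untouched.

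- **%VMSOD:** the stated conclusion is reversed, with no numerical effect. This rests on no assumption beyond the section's own definitions.
- **SF-36:** key and sample form conflict. The size (16 of 35 items, ranges of 8-88 and 10-90, unscored role responses) applies only if version 2 was administered, which the documents do not settle.
- **Table 2f:** three rows are seven days early, and the printed and derived Week 16 windows share none of their seven days. This assumes seven-day weeks throughout, as the first rows and the text imply. The effect on the treatment difference cannot be computed from the documents.

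The absence of a PCS/MCS formula from SAP 19.1 is missing detail, and the verdict does not rest on it.

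**What to change.** Before unblinding:

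1. **SAP 8.3.5:** replace higher with lower in the efficacy sentence.
2. **SAP 19.1:** confirm and state the SF-36 version on the tablet. If it is version 2, recode items 13-19 and 23-31 on five levels (0/25/50/75/100, in the direction that makes high scores favourable). For either version, add the PCS and MCS scoring. Correct the role-emotional item count in 8.3.1.1, which gives 4 against 3 in 19.1 and in Protocol 8.1.8.1.
3. **Table 2f:** set Week 16 to Days 106-112 (target 109), Week 20 to Days 134-140 (137) and Week 24 to Days 162-168 (165). Check the rows behind the ellipsis, especially Weeks 5-15. State whether diary days on or after an early Visit 7 count toward Week 16.
4. **SAP 6.4:** name the rhinosinusitis VAS as the weekly scale in the text and in Table 2f, and keep EQ-VAS under Table 2a only.

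The cost is text edits, one check of the tablet build and, if it is version 2, a corrected scoring macro. No new data are needed.

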8.3.6. FEV₁ and % Predicted FEV₁

 FEV_1 (L/min) will be obtained by spirometry at each clinic visit during the treatment period (on Day 1, Week 4, 8, 12, and 16). The FEV_1 value will be recorded in the CRF. FEV_1 and % Predicted FEV_1 will be analyzed for all subjects, as well as among subjects with comorbid asthma.

Summary statistics will be provided for all subjects, as well as for the subgroup of subjects with comorbid asthma, for baseline, each time of measurement, and for changes from baseline.

For all subjects, and again for subjects with comorbid asthma only, statistical analysis of FEV_1 and % Predicted FEV_1 will employ an MMRM where the changes from baseline at Weeks 4, 8, 12 and 16 values are modeled using the baseline (Day 1) value as a covariate; treatment (3 levels), stratification factor (for all subjects model only), treatment by stratification factor (for all subjects model only), time (Weeks 4, 8, 12, and 16), and treatment by time interaction as fixed effect factors; and subject (the repeated measures) as random effect.

Treatment comparisons between etokimab and Placebo groups will use the Week 16 least squares means and associated standard errors. Ninety-five percent confidence intervals will be obtained for both parameters, and p-values for comparison of etokimab with placebo groups will be presented.

